Adjudicated cardiovascular events for cardiovascular outcomes assessment	Cardiovascular events including core MACE (cardiovascular death, nonfatal myocardial infarction, nonfatal stroke), expanded MACE (unstable angina requiring hospitalization, transient ischemic attack, peripheral or coronary revascularization procedures, hospitalization for congestive heart failure). Other events potentially related to adverse cardiovascular outcomes as defined in Appendix E and included in the CAC charter will be sent to the CAC for adjudication.
Safety and tolerability	TEAEs, ECGs, vital signs, clinical laboratory assessments (including lipid profile changes)

ALP = alkaline phosphatase; ALT = alanine aminotransferase; AST = aspartate aminotransferase; FGF-19 = fibroblast growth factor 19; GGT = gamma-glutamyl transferase; HbA1c = hemoglobin A1c; INR = international normalized ratio; LP(a) = lipoprotein(a); MELD = model of end stage liver disease;
	
EOS Criteria for Evaluation:	
End of Study Analyses Variables	Assessments
Primary Objective Assessed at EOS (All Subjects)	
Clinical outcomes composite endpoint	Time to first occurrence of any of the following adjudicated events: death (all cause); MELD score ≥ 15 ; liver transplant; hospitalization (as defined by a stay of ≥ 24 hours) for onset of variceal bleed, hepatic encephalopathy (as defined by a West Haven score of ≥ 2), or spontaneous bacterial peritonitis (confirmed by diagnostic paracentesis); ascites secondary to cirrhosis and requiring medical

	intervention (eg, diuretics or paracentesis); or progression to cirrhosis
Secondary Objective Assessed at EOS (All Subjects)	
Improvement in fibrosis with no worsening of NASH	A reduction from baseline in fibrosis of at least 1 stage and no increase in hepatocellular ballooning, lobular inflammation or steatosis based on liver biopsy using NASH CRN criteria
Resolution of NASH with no worsening of fibrosis	NASH resolution defined as the overall histopathologic interpretation of 1) “no fatty liver disease” or 2) “fatty liver disease (simple or isolated steatosis) without steatohepatitis” AND a NAS of 0 for ballooning and 0-1 for inflammation with no increase in fibrosis stage from baseline based on liver biopsy using NASH CRN criteria

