Adjudicated cardiovascular events for cardiovascular outcomes assessment	Cardiovascular events including core MACE (cardiovascular death, nonfatal myocardial infarction, nonfatal stroke) and expanded MACE (unstable angina requiring hospitalization, transient ischemic attack, peripheral or coronary revascularization procedures, hospitalization for congestive heart failure and arrhythmias). Any hospitalization (≥24 hours) where a cause has not been identified by the Investigator will be treated as a cardiovascular event and sent for adjudication. Other events potentially related to adverse cardiovascular outcomes as defined in Appendix E in the protocol and included in the CAC charter will be sent to the CAC for adjudication
Adjudicated events of hepatic injury	Incidence of adjudicated events of hepatic injury
Adjudicated events of acute kidney injury	Incidence of adjudicated events of acute kidney injury
Long-term safety and tolerability	TEAEs, ECGs, vital signs, clinical laboratory assessments (including lipid profile changes)

ALP = alkaline phosphatase; ALT = alanine aminotransferase; [redacted]; AST = aspartate aminotransferase; [redacted]; CAC = Cardiovascular Adjudication Committee; [redacted]; ECG = electrocardiogram; [redacted]; EOS = end of study; [redacted]; MACE = major adverse cardiovascular events; MELD = model of end stage liver disease; [redacted]; NAFLD = nonalcoholic fatty liver disease; NFS = NAFLD fibrosis score; TE = transient elastography; TEAE = treatment-emergent adverse event; [redacted]
	

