Improvement in NAS by at least 2 points with no worsening of fibrosis	A reduction in NAS by at least 2 points with no increase in fibrosis stage from baseline based on liver biopsy using NASH CRN criteria
Improvement of fibrosis and resolution of NASH as a composite endpoint and as defined by both endpoints being met in the same subject	A reduction from baseline in fibrosis stage of at least 1 using NASH CRN criteria and resolution of NASH as defined above
Resolution of fibrosis	A fibrosis stage of 0 based on liver biopsy using NASH CRN criteria
Liver biochemistry and markers of liver function	ALT, AST, GGT, ALP, total and direct bilirubin, albumin, INR, and platelets

Safety Objectives at EOS (All Subjects)	
Adjudicated cardiovascular events for cardiovascular outcomes assessment	Cardiovascular events including core MACE (cardiovascular death, nonfatal myocardial infarction, nonfatal stroke) and expanded MACE (unstable angina requiring hospitalization, transient ischemic attack, peripheral or coronary revascularization procedures, hospitalization for congestive heart failure, and arrhythmias). Any hospitalization (≥ 24 hours) where a cause has not been identified by the Investigator will be treated as a cardiovascular event and sent for adjudication. Other events potentially related to adverse cardiovascular outcomes as defined in Appendix E and included in the CAC charter will be sent to the CAC for adjudication
Adjudicated events of AKI	Evaluate the effect of OCA compared to placebo on the incidence of adjudicated AKI events
Adjudicated events of hepatic injury	Evaluate the effect of OCA compared to placebo on the incidence of adjudicated events of hepatic injury
Long-term safety and tolerability	TEAEs, ECGs, vital signs, clinical laboratory assessments (including lipid profile changes)

AKI = acute kidney injury; ALT = alanine aminotransferase; [redacted]; AST = aspartate aminotransferase; [redacted]; CAC = Cardiovascular Adjudication Committee; [redacted]; ECG = electrocardiogram; [redacted]; Fibrosis; EOS = end of study; [redacted]; MACE = major adverse cardiovascular events; MELD = model of end stage liver disease; [redacted]; [redacted]; NAFLD = nonalcoholic fatty liver disease; NFS = NAFLD fibrosis score; [redacted]; TEAE = treatment-emergent adverse event; [redacted]

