16.9.3. Cardiovascular Event Adjudication

Adjudicated cardiovascular events include core MACE (cardiovascular death, nonfatal myocardial infarction, and nonfatal stroke) and expanded MACE (unstable angina requiring hospitalization, transient ischemic attack, peripheral or coronary revascularization procedures, hospitalization for congestive heart failure and arrhythmias). Any hospitalization (≥ 24 hours) where a cause has not been identified by the Investigator will be treated as a cardiovascular event and sent for adjudication. Other events potentially related to adverse cardiovascular outcomes are defined in [Appendix E](#) and will be included in the Cardiovascular Adjudication Committee (CAC) Charter for adjudication. The adjudication of these events will be handled separately from the adjudication of events for assessment of the primary endpoint in this study (See

Section 16.11). Undetermined cause of death will be classified as a cardiovascular death by the CAC.

There will be no formal hypothesis testing of MACE at the Month 18 Interim Analysis. The EOS assessment of MACE will include all MACE events occurred from the start of the study.

Summaries of adjudicated cardiovascular events will include the incidence of TEAEs, the incidence of serious TEAEs, and a time-to-event analysis as described below. All summaries of incidence will include the associated exact binomial 95% CI.

The time-to-event endpoints include:

- Time from randomization to the first confirmed occurrence of cardiovascular death, nonfatal myocardial infarction, nonfatal stroke, or nonfatal unstable angina requiring hospitalization
- Time from randomization to the confirmed occurrence of cardiovascular death (including fatal myocardial infarction, fatal stroke)
- Time from randomization to the first confirmed occurrence of myocardial infarction (nonfatal or fatal)
- Time from randomization to the first confirmed occurrence of stroke (nonfatal or fatal)
- Time from randomization to the confirmed occurrence of death from any cause
- Time from randomization to the first confirmed occurrence of unstable angina requiring hospitalization (nonfatal or fatal)
- Time from randomization to the first occurrence of coronary revascularization procedure
- Time from randomization to the first occurrence of hospitalization for congestive heart failure
- Time from randomization to the first occurrence of transient ischemic attack
- Time from randomization to the first occurrence of arrhythmia

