#### **10.4.9. Cardiovascular Risk**

##### **10.4.9.1. Adjudicated Cardiovascular Events**

Adjudicated cardiovascular events, including Major Adverse Cardiovascular Events (MACE) (defined as death, myocardial infarction, and stroke) and other related events including hospitalization for unstable angina, revascularization procedures, hospitalization for congestive heart failure, transient ischemic attack, and additional events related to adverse cardiovascular outcomes, will be included in the CEC Charter for adjudication. The adjudication of these events will be handled separately from the adjudication of events for assessment of the primary clinical composite outcome endpoint in this study.

Summaries of adjudicated cardiovascular events including MACE will include the overall summary of cardiovascular TEAEs, incidence of TEAEs, incidence of serious TEAEs, annualized adjudicated CV event rate, and a time-to-event analysis as described below. All summaries of incidence will include the associated exact binomial 95% confidence interval (CI). Summaries will be carried out for the Safety Population and ITT Population.

The time-to-event endpoints include:

- Time from randomization to the first confirmed occurrence of cardiovascular death, nonfatal myocardial infarction, nonfatal stroke
- Time from randomization to the confirmed occurrence of cardiovascular death (including fatal myocardial infarction, fatal stroke)
- Time from randomization to the first confirmed occurrence of myocardial infarction (nonfatal or fatal)

- Time from randomization to the first confirmed occurrence of stroke (nonfatal or fatal)
- Time from randomization to the confirmed occurrence of death from any cause
- Time from randomization to the first confirmed occurrence of unstable angina requiring hospitalization (nonfatal or fatal)
- Time from randomization to the first occurrence of coronary revascularization procedure
- Time from randomization to the first occurrence of hospitalization for congestive heart failure
- Time from randomization to the first occurrence of transient ischemic attack
- Time from randomization to the first occurrence of hospitalization for clinically significant arrhythmias
- Time from randomization to the first occurrence of hospitalization for peripheral revascularization procedures

In addition, subjects with any adjudicated cardiovascular event will be presented by the following lipid subgroups:

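### The SAP narrows two adjudicated cardiovascular safety endpoints, peripheral revascularization and arrhythmia, relative to the protocol, and SAP Section 11 does not record the change

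*Protocol*

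**What the plan says.** **Peripheral revascularization.** The end-of-study definition in the protocol synopsis lists "peripheral or coronary revascularization procedures, hospitalization for congestive heart failure and arrhythmias" within expanded MACE. Section 12 and Section 16.9.3 include the same component, and none of the three places a hospitalization condition on it. Appendix E defines peripheral vascular intervention as a catheter-based or open surgical procedure, recognizes elective as well as non-elective status, and does not require admission. The time-to-event list in protocol 16.9.3 has a coronary revascularization endpoint but no peripheral one. SAP 10.4.9.1 adds a peripheral endpoint, worded "Time from randomization to the first occurrence of hospitalization for peripheral revascularization procedures". Its coronary endpoint has no hospitalization condition.

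**Arrhythmia.** The definition sentence in protocol 16.9.3 reads "hospitalization for congestive heart failure and arrhythmias). Any hospitalization", as the synopsis does, so the word hospitalization can be taken to govern arrhythmias. Section 12 inserts a comma, "hospitalization for congestive heart failure, and arrhythmias", which makes arrhythmia a stand-alone item. The endpoint in 16.9.3 is "Time from randomization to the first occurrence of arrhythmia", with no condition. The SAP endpoint is "Time from randomization to the first occurrence of hospitalization for clinically significant arrhythmias". Appendix E has no arrhythmia event definition; the term appears there only within the definitions of death.

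**Change log.** SAP Section 11 cites protocol version 11.0 as the basis for the added safety objectives and notes added analyses of adjudicated cardiovascular data. It mentions neither restriction.

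**The concern.** The incidence of adjudicated cardiovascular events is a named end-of-study safety objective (protocol 6.7). Protocol 5.5 says that OCA raises LDL cholesterol, that no cardiovascular conclusion can yet be drawn, and that longer treatment in more subjects is needed. Protocol 16.9.3 specifies stratified log-rank tests, Kaplan-Meier estimates and Cox hazard ratios for these endpoints. A difference in wording therefore changes which subjects count as events in a reported comparison with placebo.

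Two programmers working in good faith, one from the protocol and one from the SAP, would produce different arrhythmia tables. The SAP programmer would also leave outpatient peripheral procedures out of the peripheral table, although the protocol treats them as expanded MACE. If the choice is left open until the data are unblinded, it can no longer be shown to be independent of the results.

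**Working it through.** The documents give no cardiovascular event rates and the plan states no figure to reproduce, so the check is a comparison of texts. Each row asks whether a given event counts under each wording.

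| Event | Protocol Section 12 | Protocol synopsis and 16.9.3 definition, if hospitalization governs arrhythmia | Protocol 16.9.3 endpoint | SAP 10.4.9.1 endpoint |
|---|---|---|---|---|
| Arrhythmia, not hospitalized | Yes | No | Yes | No |
| Arrhythmia, hospitalized, not judged clinically significant | Yes | Yes | Yes | No |
| Arrhythmia, hospitalized and clinically significant | Yes | Yes | Yes | Yes |
| Peripheral procedure, outpatient | Yes | Yes | None listed | No |
| Peripheral procedure with hospitalization for it | Yes | Yes | None listed | Yes |
| Coronary revascularization, outpatient | Yes | Yes | Yes | Yes |

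1. **Arrhythmia sets are nested.** Hospitalized and clinically significant arrhythmias are a subset of hospitalized arrhythmias, which are a subset of all arrhythmias. The SAP endpoint uses the smallest set and the protocol endpoint the largest. The SAP event count can only be equal or lower, and a subject's first qualifying date can only be the same or later.
2. **Peripheral sets are nested.** Procedures with hospitalization are a subset of all procedures. The SAP endpoint uses the subset; protocol expanded MACE and Appendix E use the full set.
3. **The SAP is not consistent within its own list.** An outpatient coronary procedure counts and an outpatient peripheral one does not. No reason is given.
4. **Protocol 16.9.3 is not consistent within itself on arrhythmia.** Its definition sentence can be read as requiring hospitalization, while its endpoint does not. The conflict therefore does not rest only on the comma in Section 12.
5. **Non-hospitalized arrhythmias can come to light.** Protocol 15.2.4 has clinically significant ECG abnormalities reported as adverse events, and ECGs continue through the study under Table 1. The first row of the table is not an empty category.
6. **The difference is not explained by version lag.** SAP Section 11 refers to protocol version 11.0, which already contains the arrhythmia endpoint.

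**The case against.** The strongest reply is that the adjudication charter governs. Protocol 16.11 and SAP 6.4.3 place the details of adjudicated events in the charters, and the protocol's summary of changes says that the 16.9.3 definition was updated to agree with the cardiovascular charter. All events are reviewed by committee before any analysis. The charter is not among the documents, and it may well settle the total adjudicated count. It governs what is sent and confirmed, however. It does not say which confirmed events enter two endpoints that the protocol and SAP word differently.

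Four further limits stand:

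- The event list in SAP 10.4.9.1 is open-ended and names revascularization procedures without a hospitalization condition. Arrhythmia is unnamed there rather than excluded, and outpatient peripheral procedures can still appear in the overall adjudicated summaries. They are lost only from the peripheral time-to-event endpoint.
- Neither document lists a time-to-first-expanded-MACE endpoint, and the SAP does not use that term. A reader might infer that arrhythmias would dilute an ischemic composite. The listed composites contain cardiovascular death, myocardial infarction and stroke (with unstable angina in the protocol), so arrhythmia does not enter them.
- The absence of arrhythmia from the Month 18 list, "peripheral or coronary revascularization procedures, hospitalization for congestive heart failure). Other events potentially related", might look like another contradiction. Arrhythmia was added in protocol version 11.0, after the Month 18 analysis for the original submission, so a different list is expected.
- The any-arrhythmia reading rests on one comma and one short endpoint line. Most of the text is compatible with hospitalization for arrhythmia. This bears on which wording to adopt; it does not remove the conflict.

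SAP Section 10 also plans no inferential safety comparison unless specified. That lowers the stakes but leaves the estimates and tables dependent on the definition.

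**Conclusion.** The conflict is real and confined to two component safety endpoints. For peripheral revascularization, the SAP endpoint omits outpatient procedures that the protocol and Appendix E count. For arrhythmia, the SAP adds two conditions that the protocol endpoint lacks, and the protocol's own statements differ. In both cases the SAP count is equal to or lower than the protocol's, and SAP Section 11 does not disclose the restriction.

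The size is unknown. Any multiple would have to come from assumed arrhythmia rates and follow-up, and would reflect those assumptions rather than anything in the documents. A reader might also conclude that the whole adjudicated cardiovascular count depends on which sentence is programmed. The documents do not show that, because the charter may fix the total. The primary endpoint, alpha, sample size and the core MACE components are not affected by this point. The conclusion rests on the wording alone and assumes that no unseen document already defines these two endpoints for programming. It is worth correcting because the safety question matters for this drug and the correction is cheap.

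**What to change.** Before unblinding:

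1. In SAP 10.4.9.1, remove the hospitalization condition from the peripheral revascularization endpoint so that it matches the coronary endpoint and Appendix E. Add the same endpoint to the time-to-event list in protocol 16.9.3.
2. Use one arrhythmia wording, aligned with the cardiovascular adjudication charter, in the synopsis, Section 12, Section 16.9.3 and SAP 10.4.9.1. Hospitalization for arrhythmia fits most of the existing text. If clinical significance is kept, define it, or cite the charter definition. Report non-hospitalized arrhythmias as adverse events.
3. If the sponsor intends either SAP restriction, state it with its reason in SAP Section 11.

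No new composite analysis is needed. The cost is wording in both documents and minor programming, with no new data collection. The downside of the suggested arrhythmia wording is that non-hospitalized arrhythmias are absent from the time-to-event endpoint and appear only in the adverse-event tables. A different single definition would also resolve the point, provided that it is fixed in advance and used everywhere.

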4. LIST OF ABBREVIATIONS AND DEFINITIONS OF TERMS

The following abbreviations and specialist terms are used in this protocol.

Abbreviation or Specialist Term	Explanation
A1AT	alpha-1-antitrypsin
ADA	American Diabetes Association
AE	adverse event
AFP	alpha-fetoprotein
AKI	acute kidney injury
ALP	alkaline phosphatase
ALT	alanine aminotransferase
ANCOVA	analysis of covariance
[REDACTED]	[REDACTED]
AUDIT	Alcohol Use Disorders Identification Test
[REDACTED]	[REDACTED]
BAS	bile acid sequestrants
β-hCG	beta human chorionic gonadotropin
BMI	body mass index
BNP	B-type natriuretic peptide
BUN	blood urea nitrogen
[REDACTED]	[REDACTED]
CI	confidence interval
[REDACTED]	[REDACTED]
CMH	Cochran–Mantel–Haenszel
CP	Child-Pugh
CRA	Clinical Research Associate
CRF	case report form
CRN	Clinical Research Network
CS	clinically significant
CTCAE	Common Terminology Criteria for Adverse Events

Abbreviation or Specialist Term	Explanation
DAP	data access plan
DILI	drug-induced liver injury
DMC	Data Monitoring Committee
DNA	deoxyribonucleic acid
EASD	European Association of the Study of Diabetes
ECG	electrocardiogram
eCRF	electronic case report form
eGFR	estimated glomerular filtration rate
EDC	electronic data capture
EGD	esophagogastroduodenoscopy
█	█
EOS	end of study
EOT	End of Treatment
FDA	Food and Drug Administration
█	█
█	█
FLINT	F arnesoid X receptor L igand O CA i n N onalcoholic Steatohepatitis T reatment
FRS	Framingham Risk Score
FXR	farnesoid X receptor
GCP	Good Clinical Practice
GGT	gamma-glutamyl transferase
h	hours
HbA1c	hemoglobin A1c
HBsAg	hepatitis B surface antigen
█	█
HCP	healthcare provider
HCV	hepatitis C virus
HDLc	high-density lipoprotein cholesterol
█	█
█	█
HSAC	Hepatic Safety Adjudication Committee
IB	Investigator's Brochure
ICF	informed consent form
ICH	International Conference on Harmonisation

Abbreviation or Specialist Term	Explanation
ICMJE	International Committee of Medical Journal Editors
IEC	Independent Ethics Committee
IIEF-15	International Index of Erectile Function
IL-6	interleukin-6
IND	investigational new drug
INR	international normalized ratio
IRB	Institutional Review Board
ISF	Investigator site file
ITT	Intent-to-Treat
IWRS	interactive web response system
IWQoL-Lite	Impact of Weight on Quality of Life-Lite
KM	Kaplan-Meier
LDLc	low-density lipoprotein cholesterol
LP(a)	lipoprotein(a)
LS	least-square
LTF	lost to follow-up
MACE	major adverse cardiovascular events
MCH	mean corpuscular hemoglobin
MCHC	mean corpuscular hemoglobin concentration
MCV	mean corpuscular volume
MedDRA	Medical Dictionary for Regulatory Activities
MELD	model of end stage liver disease
■	■
■	■
MW	molecular weight
NAFLD	nonalcoholic fatty liver disease
NAS	nonalcoholic fatty liver disease activity score
NASH	nonalcoholic steatohepatitis
NCS	not clinically significant
NFS	nonalcoholic fatty liver disease fibrosis score
OCA	obeticholic acid
PAI-1	plasminogen activator inhibitor-1
PBC	primary biliary cirrhosis or primary biliary cholangitis
■	■

Abbreviation or Specialist Term	Explanation
PCSK9	proprotein convertase subtilisin/kexin type 9
█	██████████
█	██████████
PLIN2	perilipin 2
PNPLA3	patatin-like phospholipase domain-containing protein, 3
PP	per protocol
PSC	primary sclerosing cholangitis
PT	prothrombin time
PTT	partial thromboplastin time
QTcF	QT interval corrected by the Fridericia's formula
RNA	ribonucleic acid
RR	time between 2 consecutive R waves
SAE	serious adverse event
█	██████████
SAMM50	sorting and assembly machinery component 50 homolog
SAP	statistical analysis plan
SAR	suspected adverse reaction
█	██████████
SUSAR	suspected unexpected serious adverse reaction
T3	triiodothyronine
T4	thyroxine
TE	transient elastography
█	██████████
TM6SF2	transmembrane 6 superfamily 2
TNF- α	tumor necrosis factor- α
TSH	thyroid stimulating hormone
TZD	thiazolidinedione
ULN	upper limit of normal
VAS	visual analogue scales
█	██████████
wks	Weeks
█	██████████

